13.4. Sponsor Responsibilities

All information and data sent to BSC concerning subjects or their participation in this study will be considered confidential by BSC and will be kept confidential in accordance with all applicable laws and regulations. Only authorized BSC personnel and/or a BSC representative including, but not limited to Contract Research Organization (CRO), will have access to this information. Authorized regulatory personnel have the right to inspect and copy all records pertinent to this study. Study data collected during this study may be used by BSC for the purposes of this study, publication, and to support future research and/or other business purposes, such as overseeing and improving the performance of its device, new medical research and proposals for developing new medical products and procedures. All data used in the analysis and reporting of this study or shared with a third-party researcher will be without identifiable reference to specific subjects.

Information received during the study will not be used to market to subjects; subject names will not be placed on any mailing lists or sold to anyone for marketing purposes.

13.4.1. Role of Boston Scientific Representatives

Boston Scientific personnel can provide technical support to the investigator and other health care personnel (collectively HCP) as needed. Support may include, but is not limited to, HCP training, addressing HCP questions, or providing clarifications to HCPs concerning the operation of BSC equipment/devices (including programmers, analyzers, and other support equipment).

At the request of the investigator and while under investigator supervision, BSC personnel may operate equipment, assist with the conduct of testing specified in the protocol, and interact with the subject to accomplish requested activities.

Typical tasks may include the following:

- Provide instructions for the safe return of products. For potentially hazardous items, provide specialized instructions and materials, as applicable.

- Clarifying device behavior, operation or diagnostic output as requested by the investigator or other health care personnel
- Entering technical data on technical source form as long as the responsible investigator verifies and signs the completed form
- Provide technical expertise/support to subjects during office visits and/or during teleconference calls/electronic communications with the principal investigator or their delegated site staff and the subject.

In addition, BSC personnel may perform certain activities to ensure study quality. These activities may include the following.

- Observing testing or medical procedures to provide information relevant to protocol compliance
- Reviewing collected data and study documentation for completeness and accuracy

Boston Scientific personnel will not do the following.

- Practice medicine
- Provide medical diagnosis or treatment to subjects
- Discuss a subject's condition or treatment with a subject
- Independently collect critical study data (defined as primary or secondary endpoint data)
- Enter data in electronic data capture systems or on paper case report forms

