4.1. Justification for the Study Design

The study is designed to demonstrate that physicians are able to complete standard of care ERCP procedures and other duodenoscope-based procedures with the Exalt Model D single-use duodenoscope. The Exalt duodenoscope is designed to perform similarly to conventional marketed reusable duodenoscopes.

5. Subject Selection

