7.2.1. Strategies for Recruitment and Retention

All patients under the care of a study investigator during the enrollment period of a site will be considered for recruitment.

7.3. *Informed Consent*

Data collection and/or study procedure will not occur prior to the subject signing the ICF. Patients will be considered enrolled in the study once they sign the informed consent. Once a subject is considered enrolled in the study, baseline information may be obtained.

7.4. *Baseline*

Baseline information will include the following data points: age at time of consent, gender, and relevant medical history.

7.5. *Index Procedure*

During the index procedure, the endoscopist or designated member of study staff will record: start and stop times of procedure, scope information, whether certain types of medicine were administered, and any activities completed or attempted during the procedure, regardless of original intent. Any ensuing device events will be recorded and reported.

After the ERCP procedure has been completed, the endoscopist will rate their experience using the Exalt device during the index procedure.

7.6. *72 hour (-1 day, + 2 days) and 30 day (± 3 days) Assessments*

All enrolled subjects will be seen in person or evaluated via telephone to screen for any post-procedure adverse events, and to evaluate the resolution of any previously noted adverse events or sequelae, as applicable.

7.7. *Study Completion*

Subjects will be followed for 30 days (± 3 days) post index procedure. Subjects will continue to receive care from their doctor as they normally would. At study completion, an End of Study form will be completed, indicating whether the subject completed the study. If the last follow-up visit was not completed, the reason will be noted on the study completion form (e.g. subject withdrawn by investigator, subject withdrew consent, lost to follow-up, AE, death, etc.).

7.8. *Source Documents*

It is preferable that original source documents are maintained, when available. In lieu of original source documents, certified copies are required to be maintained. A certified copy is a copy (irrespective of the type of media used) of the original record that has been verified

(i.e., by a dated signature or by generation through a validated process) to have the same information, including data that describe the context, content, and structure, as the original.

8. Statistical Considerations

8.1. *Statistical Hypothesis and sample size justification*

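### The plan permits sponsor personnel to support index procedures, but the protocol lists no item recording when they did and does not keep them away from the endoscopist's rating

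*Combined protocol and SAP*

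**What the plan says.** **What is permitted.** Section 13.4.1 (Role of Boston Scientific Representatives) opens with a general permission: "Boston Scientific personnel can provide technical support to the investigator and other health care personnel (collectively HCP) as needed". It then adds that, if the investigator asks and "while under investigator supervision, BSC personnel may operate equipment, assist with the conduct of testing specified in the protocol". Typical tasks include explaining how the device behaves and operates. A separate list of study-quality activities includes "Observing testing or medical procedures to provide information relevant to protocol compliance".

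**What is barred.** The same section says sponsor staff will not practise medicine, diagnose or treat subjects, collect primary or secondary endpoint data independently, or enter data in EDC or on paper CRFs.

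**What is recorded.** Under section 7.5 (Index Procedure), "the endoscopist or designated member of study staff will record: start and stop times of procedure, scope information", certain medicines, and "any activities completed or attempted during the procedure, regardless of original intent". Device events are also recorded. Table 7-1 adds maneuvers, the Exalt Evaluation, and the device event and adverse event assessments. Once the procedure is over, "the endoscopist will rate their experience using the Exalt device during the index procedure".

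**What is analysed.** Section 8.3.2 summarises procedure data, including the qualitative evaluation, with descriptive statistics. It names no subgroup.

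**The concern.** Section 4.1 gives the purpose: "The study is designed to demonstrate that physicians are able to complete standard of care ERCP procedures" and other duodenoscope-based procedures with Exalt. Table 3-1 treats completing the index procedure with Exalt as an indicator of device performance (the reason given for the crossover endpoint), and the rating as a subjective evaluation by the intended users.

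Both can be influenced by someone from the manufacturer in the room. Help with the controller or advice on device behaviour could avert a switch to a reusable scope. A rating against marketed reusable scopes could be kinder if a manufacturer's representative is present when it is given. There is no comparator arm, so no other feature of the design would reveal such an effect. If support is not recorded at the time, it will be hard to reconstruct later, and a reader could not tell how much of the experience was supported.

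**Working it through.** The plan has no hypothesis, power or sample-size calculation (section 8.1), so there is no design figure to reproduce. The check is a comparison of sections, followed by an illustration of scale.

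**1. Permission against data items.**

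- Support and operation of equipment: permitted in 13.4.1. Of the items in 7.5 and Table 7-1, the nearest is the activities item, which asks what was done or attempted, not who helped.
- Presence: observation is permitted in 13.4.1. No listed item records attendance.
- Rating: 7.5 places it after the procedure. Neither 7.5 nor 13.4.1 says who may be present.
- Nearest related record: a technical source form in 13.4.1, which sponsor staff may fill in and the investigator signs. It concerns technical data, and is not described as a case-by-case log of attendance or help.
- Safeguards: the bars in 13.4.1 protect clinical care and data handling. They do not address influence on the event being recorded or on the opinion being given.

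**2. Which endpoints are exposed.** In the earlier series described in section 1.2, whose primary endpoint has the same wording as the synopsis, all 60 procedures counted as completed: 58/60 = 96.7% with the single-use scope only and 2/60 = 3.3% with crossover. If completion is counted that way here, averting a crossover changes the crossover rate and leaves completion unchanged. The exposed endpoints are then crossover and the rating.

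**3. Illustration for crossover.** Let s be the supported share, and p_s and p_u the crossover rates with and without support.

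Pooled rate = s × p_s + (1 − s) × p_u

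Pooled rate minus unsupported rate = s × (p_s − p_u)

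None of s, p_s or p_u is in the documents; all are assumptions. The 3.3% row borrows the rate from the earlier series.

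| p_s, p_u | s = 25% | s = 50% | s = 75% |
|---|---|---|---|
| 2%, 5% | 4.25% (−0.75) | 3.5% (−1.5) | 2.75% (−2.25) |
| 2%, 8% | 6.5% (−1.5) | 5.0% (−3.0) | 3.5% (−4.5) |
| 3.3%, 3.3% | 3.3% (0) | 3.3% (0) | 3.3% (0) |
| 5%, 2% | 2.75% (+0.75) | 3.5% (+1.5) | 4.25% (+2.25) |

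Figures in brackets are percentage points relative to the unsupported rate. Example: 0.5 × 2% + 0.5 × 5% = 3.5%, and 3.5% − 5% = −1.5 points. The last row covers help being called for mainly in difficult cases.

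**4. Scale.** With 1000 subjects and 33 crossovers (again borrowing 3.3%), the exact 95% interval is 2.3% to 4.6%, about 1.2 points either side. The larger gaps in the table exceed that; the smallest non-zero ones do not.

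**5. What a breakdown could show.** If support were recorded, comparing 2% with 5% in 1000 subjects (two-sided 5% level) has about 73% power at a 50:50 split, 54% at 25:75 and 19% at 10:90 (supported:unsupported). A breakdown would be mainly descriptive.

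No comparable calculation is possible for the rating, because the documents do not give its scale.

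**The case against.** A reader might infer that the endpoints do mix supported and unsupported use, and that crossover is therefore understated. The documents do not support that.

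- **Frequency is unknown.** Section 13.4.1 grants permissions and reports no practice. Its mention of programmers and analyzers, and of supporting subjects at office visits, suggests general template text. No section shows sponsor staff attending any index procedure. This stands.
- **The permissions are limited and separate.** Operating equipment needs the investigator's request and supervision. Observation is for protocol compliance, not for troubleshooting. This stands, but general technical support has no stated limit on timing or amount.
- **The forms were not supplied.** The index eCRF, the Exalt Evaluation form and the monitoring plan are outside the documents and may hold such a field. The claim is only that the protocol text lists none.
- **The target is not stated.** Section 4.1 speaks of standard of care procedures; nothing says that routine use is without manufacturer support. This stands. It is a reason to report the supported share, so that readers can judge the setting themselves.
- **The direction is not known.** Help given on request may cluster in difficult cases or with newer users, so supported cases could show more crossover. For the same reason, a supported-versus-unsupported table is confounded and cannot say what supported cases would have done without help. This stands and limits what the fix can claim.
- **The study is descriptive.** No planned figure depends on this point. That limits its weight, but a descriptive study also relies on describing the conditions of use.

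**Conclusion.** The concern holds as a gap in recording and in protection of the rating. The plan allows sponsor involvement in the index procedure; the protocol text neither requires it to be recorded nor separates it in the analysis, and does not keep sponsor staff away while the endoscopist rates the device. Crossover and the rating could reflect manufacturer support in an unknown share of cases.

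Its size cannot be stated from the documents. Across the assumed values above, the gap between pooled and unsupported crossover runs from −4.5 to +2.25 points and includes zero. Those rates and shares are illustrations, not estimates. Completion may be unaffected, on the assumption that crossovers count as completed as they did in the earlier series. It would be wrong to conclude that the results are biased in the device's favour, or that the analysts certainly cannot identify supported cases.

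The change is worth making because it is specific and cheap, protects a subjective secondary endpoint, and captures information that is hard to recover later.

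**What to change.** 1. In 13.4.1 and 7.5, state that the Exalt Evaluation is completed without sponsor personnel present.
2. On the index eCRF, unless already there, add whether sponsor personnel were present (yes/no) and, if so, the type of help given: none, advice, or operation of equipment. Keeping presence apart from help matters, because the first bears mainly on the rating and the second on crossover. List the items in 7.5 and Table 7-1.
3. In 8.3.2, report the share of supported cases and tabulate crossover, ratings and completion by support. Label this a descriptive breakdown, and say that support is requested rather than assigned, so a difference between the groups is not an effect of support.

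If the eCRF already holds these fields, only the sentence on the rating, the reference to the fields and the table are needed.

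**Cost.** A small burden per case, and a protocol amendment that needs IRB/EC/REB approval before it takes effect (section 13.3), at up to 40 sites. Cases treated before the change would lack the field and should be shown as not recorded, not counted as unsupported.

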13.5. Insurance

Where required by local/country regulation, proof and type of insurance coverage, by BSC for subjects in the study will be obtained.

14. Monitoring

Monitoring will be performed during the study to assess continued compliance with the protocol and applicable regulations. In addition, the clinical research monitor verifies that study records are adequately maintained, that data are reported in a satisfactory manner with respect to timeliness, adequacy, and accuracy, and that the Principal Investigator continues to have sufficient staff and facilities to conduct the study safely and effectively. The Principal Investigator/institution guarantees direct access to original source documents by BSC personnel, their designees, and appropriate regulatory authorities.

The sponsor will put a plan in place to document the specific monitoring requirements.

The study may also be subject to a quality assurance audit by BSC or its designees, as well as inspection by appropriate regulatory authorities. It is important that the Principal Investigator and relevant study personnel are available during on-site monitoring visits or audits and that sufficient time is devoted to the process.

15. Potential Risks and Benefits

15.1. *Instructions for Use*

Please refer to the Instructions for Use for an overview of anticipated (device) effects, and risks associated to the study device(s).

15.2. *Risks Associated with Participation in the Clinical Study*

Risk associated with participation in the Clinical Study are similar to that of an ERCP with standard duodenoscope. Participation in the trial may be time consuming.

15.3. *Risk Minimization Actions*

Additional risks may exist. Risks can be minimized through compliance with this protocol, performing procedures in the appropriate hospital environment, adherence to subject selection criteria, close monitoring of the subject's physiologic status during research procedures and/or follow-ups and by promptly supplying BSC with all pertinent information required by this protocol.

15.4. *Anticipated Benefits*

Recent literature has identified an outbreak with carbapenem-resistant Enterobacteriaceae (CRE).³⁻⁸ That endoscopic transmission of infection can be prevented by strict adherence to disinfection protocols has been challenged with no clearly identified protocol to reduce this risk.¹³ Use of a Single-Use Duodenoscope would alleviate the need for high level disinfection of the standard Duodenoscope, thereby reducing the risk of infection transmission between patients.

15.5. *Risk to Benefit Rationale*

Based on collected reports in literature to-date, the risk-to-benefit ratio is within reason for foreseeable risks. However, literature reports do not always capture all side effects. Observation and follow-up of patients is required as outlined in the protocol.

16. Safety Reporting

16.1. *Reportable Events by Investigational Site to Boston Scientific*

It is the responsibility of the investigator to assess and report to BSC any event which occurs in any of following categories:

- All Non-Serious Adverse Events
- All Serious Adverse Events
- All Study Device Deficiencies

- Unanticipated Adverse Device Effects/Unanticipated Serious Adverse Device Effects
- New findings/updates in relation to already reported events

When possible, the medical diagnosis should be reported as the Event Term instead of individual symptoms.

If it is unclear whether or not an event fits one of the above categories, or if the event cannot be isolated from the device or procedure, it should be submitted as an adverse event and/or device deficiency.

Any reportable event, experienced by the study subject after informed consent and once considered enrolled in the study (as defined in study subject classification section), whether during or subsequent to the procedure, must be recorded in the eCRF.

Underlying diseases and chronic conditions are not reported as AEs unless there is an increase in severity or frequency during the course of the investigation. Death should not be recorded as an AE, but should only be reflected as an outcome of one (1) specific SAE (see Table 16-1 for AE definitions).

Refer to Section 15 for the known risks associated with the study device(s).

16.2. Definitions and Classification

Adverse event definitions are provided in Table 16-1. Administrative edits were made on the safety definitions from ISO 14155 and EU 2017/745 for clarification purposes.

Table 16-1: Safety Definitions

Term	Definition
Adverse Event (AE) Ref: ISO 14155 Ref: MDCG 2020-10/1	Any untoward medical occurrence, unintended disease or injury, or any untoward clinical signs (including an abnormal laboratory finding) in subjects, users or other persons, in the context of a clinical investigation, whether or not related to the study medical device and whether anticipated or unanticipated. NOTE 1: This includes events related to the study medical device or comparator. NOTE 2: This definition includes events related to the procedures involved. NOTE 3: For users or other persons, this definition is restricted to events related to the study medical device.
Adverse Device Effect (ADE) Ref: ISO 14155 Ref: MDCG 2020-10/1	Adverse event related to the use of an study medical device NOTE 1: This includes any adverse event resulting from insufficiencies or inadequacies in the instructions for use, the deployment, the implantation, the installation, the operation, or any malfunction of the study medical device. NOTE 2: This definition includes any event resulting from use error or from intentional misuse of the study medical device. NOTE 3: This includes ‘comparator’ if the comparator is a medical device.

Table 16-1: Safety Definitions

Term	Definition
Serious Adverse Event (SAE) Ref: ISO 14155 Ref: MDCG 2020-10/1	Adverse event that led to any of the following: a) death, b) serious deterioration in the health of the subject, user or other persons as defined by either: 1) a life-threatening illness or injury, or 2) a permanent impairment of a body structure or a body function, including chronic diseases, or 3) in-patient hospitalization or prolongation of existing hospitalization, or 4) medical or surgical intervention to prevent life-threatening illness or injury or permanent impairment to a body structure or a body function c) foetal distress, foetal death, or a congenital abnormality or birth defect including physical or mental impairment. NOTE 1: Planned hospitalization for a pre-existing condition, or a procedure required by the clinical investigational plan, without a serious deterioration in health, is not considered a serious adverse event.
Serious Adverse Device Effect (SADE) Ref: ISO 14155 Ref: MDCG 2020-10/1	Adverse device effect that has resulted in any of the consequences characteristic of a serious adverse event.
Unanticipated Adverse Device Effect (UADE) Ref: 21 CFR Part 812	Any serious adverse effect on health or safety or any life-threatening problem or death caused by, or associated with, a device, if that effect, problem, or death was not previously identified in nature, severity, or degree of incidence in the investigational plan or application (including a supplementary plan or application), or any other unanticipated serious problem associated with a device that relates to the rights, safety, or welfare of subjects.
Unanticipated Serious Adverse Device Effect (USADE) Ref: ISO 14155 Ref: MDCG 2020-10/1	Serious adverse device effect which by its nature, incidence, severity, or outcome has not been identified in the current risk assessment. NOTE 1: Anticipated serious adverse device effect (ASADE) is an effect which by its nature, incidence, severity or outcome has been identified in the risk assessment.
Serious Health Threat Ref: ISO 14155	Signal from any adverse event or device deficiency that indicates an imminent risk of death or a serious deterioration in the health in subjects, users or other persons, and that requires prompt remedial action for other subjects, users or other persons. NOTE 1: This would include events that are of significant and unexpected nature such that they become alarming as a potential serious health hazard or possibility of multiple deaths occurring at short intervals.

Table 16-1: Safety Definitions

Term	Definition
Device Deficiency Ref: ISO 14155 Ref: MDCG 2020-10/1	An inadequacy of a medical device related to its identity, quality, durability, reliability, usability, safety or performance. NOTE 1: Device deficiencies include malfunctions, use errors, and inadequacy in the information supplied by the manufacturer including labelling. NOTE 2: This definition includes device deficiencies related to the investigational medical device or the comparator.
The following definitions will be used for defining hospitalization or prolongation of hospitalization for SAE classification purposes:	
Hospitalizations	Hospitalization does not include: 
 • emergency room visit that does not result in in-patient admission Note: although an emergency room visit does not itself meet the definition for hospitalization, it may meet other serious criteria (e.g. medical or surgical intervention to prevent permanent impairment or damage) • elective and pre-planned treatment/surgery for a pre-existing condition that is documented in the subject's record at the time of consent/enrollment • admission for social reasons and/or respite care in the absence of any deterioration in the subject's general condition (e.g. subject is homeless, caregiver relief) • pre-planned, protocol-specified admission related to the clinical study (e.g. procedure required by protocol)
Prolongation of hospitalization	In-patient admission to the hospital that is prolonged beyond the expected standard duration for the condition under treatment. Note: new adverse events occurring during the hospitalization are evaluated to determine if they prolonged hospitalization or meet other SAE criteria.

